## 3.2 Exclusion Criteria

Participants who exhibit any of the following conditions at screening will not be eligible for admission into the study.

3.2.1 Participants may not have had other anti-neoplastic therapies within the following timelines:

- Radiation within 2 weeks
- Cytotoxic chemotherapy or monoclonal antibodies within 2 weeks, if all treatment-related toxicities have resolved to  $\leq$  grade 1 prior to starting study treatment.
- EGFR tyrosine kinase inhibitor within 2 weeks
- Any other small molecule inhibitor within 2 weeks or 5 half-lives of the compound, whichever is shorter
- Experimental treatment of any type within 30 days

3.2.2 Participants may not be currently receiving any other experimental agents.

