### 3. PARTICIPANT SELECTION

#### 3.1 Eligibility Criteria

Participants must meet the following criteria on screening examination to be eligible to participate in the study:

- 3.1.1 Participants must have histologically or cytologically confirmed stage IV or recurrent non-small cell lung cancer with a documented exon 20 insertion mutation in *EGFR* (exon 20 insertion/deletion and deletion mutations will also be allowed)
- 3.1.2 Participants must have measurable disease by RECIST 1.1
- 3.1.3 Patients must have received at least one prior line of therapy for their advanced lung cancer but there is no restrictions on the maximum number of prior therapies allowed.
- 3.1.4 Age  $\geq$  18 years.
- 3.1.5 Life expectancy  $\geq$  12 weeks.
- 3.1.6 ECOG performance status  $\leq$  2 (see Appendix A)
- 3.1.7 Participants must have normal organ and marrow function as defined below:
  - Hematologic:
    - Absolute Neutrophil Count (ANC)  $\geq 1.5 \times 10^9/L$
    - Hemoglobin (Hgb)  $\geq 8 \text{ g/dL}$
    - Platelets (plt)  $\geq 100 \times 10^9/L$
  - Biochemistry:
    - Potassium within normal limits or correctable with supplements
    - Magnesium  $>$  LLN or correctable with supplements
    - Calcium (after correction for albumin level)  $>$  LLN or correctable with supplements
  - Liver and Kidney Functions
    - AST/SGOT and ALT/SGPT  $\leq 3.0 \times$  Upper Limit of Normal (ULN) or  $\leq 5.0 \times$  Upper Limit of Normal (ULN) if liver metastases are present
    - Serum bilirubin  $\leq 1.5 \times$  ULN
    - Serum creatinine  $\leq 1.5 \times$  ULN or 24-hour clearance  $\geq 50 \text{ ml/min}$

3.1.8 The effects of AUY922 on the developing human fetus are unknown. For this reason women of child-bearing potential and men must agree to use adequate contraception (hormonal or barrier method of birth control; abstinence) prior to study entry and for the duration of study participation. Should a woman become pregnant or suspect she is pregnant while participating in this study, she should inform her treating physician immediately. In addition, women of child-bearing potential must have a documented negative serum pregnancy test. The serum pregnancy test must be obtained prior to the first administration of AUY922 ( $\leq$  72 hours prior to dosing) in all pre-menopausal women and women  $<2$  years after the onset of menopause.

3.1.9 Ability to understand and the willingness to sign a written informed consent document.

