**that are asymptomatic and clinically stable for two weeks will be eligible for protocol participation.**

- 3.2.5 History of allergic reactions attributed to compounds of similar chemical or biologic composition to AUY922
- 3.2.6 Unresolved diarrhea  $\geq$  CTCAE version 4, grade 1.
- 3.2.7 Pregnant or lactating women
- 3.2.8 Participants who have undergone any major surgery  $\leq$  2 weeks prior to starting study drug or who have not recovered from side effects of such therapy
- 3.2.9 Participants with known disorders due to a deficiency in bilirubin glucuronidation (e.g. Gilbert's syndrome).
- 3.2.10 Participants requiring the use of therapeutic doses of warfarin (Coumadin).
- 3.2.11 Participants with any of the following cardiac conditions:
  - History of long QT syndrome.
  - QTcF  $\geq$  450 ms during screening ECG.
  - History of clinically manifest ischemic heart disease including myocardial infarction, stable or unstable angina pectoris, coronary arteriography or cardiac stress testing/imaging with findings consistent with infarction or clinically significant coronary occlusion  $\leq$  6 months prior to study start.
  - History of heart failure or left ventricular (LV) dysfunction (LVEF  $\leq$  45%) by MUGA or ECHO.
  - Clinically significant ECG abnormalities including one or more of the following: left bundle branch block (LBBB), right bundle branch block (RBBB) with left anterior hemiblock (LAHB). ST segment elevations or depressions  $>$  1mm, or 2nd (Mobitz II) or 3rd degree AV block.
  - History and presence of atrial fibrillation, atrial flutter or ventricular arrhythmias including ventricular tachycardia or Torsades de Pointes.
  - Other clinically significant heart disease (e.g. congestive heart failure, uncontrolled hypertension, history of labile hypertension, or history of poor compliance with an hypertensive regimen).
  - Clinically significant resting bradycardia (<50 beats per minute).
  - Patients who are currently receiving treatment with any medication which has a relative risk or prolonging the QTc interval or inducing Torsades de Pointes (as listed in protocol section 5.4) and cannot be switched or discontinued to an alternative drug prior to commencing AUY922 dosing.
  - Patients who are on a cardiac pacemaker.

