## **4. REGISTRATION PROCEDURES**

### **4.1 General Guidelines for DF/HCC and DF/PCC Institutions**

Institutions will register eligible participants with the DF/HCC Quality Assurance Office for Clinical Trials (QACT) central registration system. Registration must occur prior to the initiation of therapy. Any participant not registered to the protocol before treatment begins will be considered ineligible and registration will be denied.

A member of the study team will confirm eligibility criteria and complete the protocol-specific eligibility checklist.

Following registration, participants may begin protocol treatment. Issues that would cause treatment delays should be discussed with the Principal Investigator. If a participant does not receive protocol therapy following registration, the participant's protocol status must be changed. Notify the QACT Registrar of participant status changes as soon as possible.

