### **4.2 Registration Process for DF/HCC and DF/PCC Institutions**

The QACT registration staff is accessible on Monday through Friday, from 8:00 AM to 5:00 PM Eastern Standard Time. In emergency situations when a participant must begin treatment during off-hours or holidays, call the QACT registration line at [REDACTED] and follow the instructions for registering participants after hours.

The registration procedures are as follows:

1. Obtain written informed consent from the participant prior to the performance of any study related procedures or assessments.
2. Complete the protocol-specific eligibility checklist using the eligibility assessment documented in the participant's medical/research record. **To be eligible for registration to the study, the participant must meet each inclusion and exclusion criteria listed on the eligibility checklist.**

**Reminder:** Confirm eligibility for ancillary studies at the same time as eligibility for the treatment study. Registration to both treatment and ancillary studies will not be completed if eligibility requirements are not met for all studies.

3. Fax the eligibility checklist(s) and all pages of the consent form(s) to the QACT at [REDACTED]

**Exception:** DF/PCC Affiliate sites must fax the entire signed consent form including HIPAA Privacy Authorization and the eligibility checklist to the Network Affiliate Office. The Network Affiliate Office will register the participant with the QACT.

4. The QACT Registrar will (a) validate eligibility, (b) register the participant on the study, and (c) randomize the participant when applicable.
5. The QACT Registrar will send an email confirmation of the registration and/or randomization to the person initiating the registration immediately following the registration and/or randomization.

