## **5.1 Pre-treatment Criteria**

### **5.1.1 Cycle 1, Day 1**

The patient should continue to meet all eligibility criteria on C1D1, as they did during the screening period.

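### Section 3.2.1 attaches its recovery condition to an exclusion, so as written it does not bar recently treated patients with unresolved toxicity

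*Combined protocol and SAP*

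**What the plan says.** Section 3.2 lists conditions that bar entry. Item 3.2.1 opens as a prohibition: "Participants may not have had other anti-neoplastic therapies within the following timelines". Its chemotherapy and antibody entry then reads "Cytotoxic chemotherapy or monoclonal antibodies within 2 weeks, if all treatment-related toxicities have resolved to" grade 1 or lower before study treatment starts. The radiation and EGFR tyrosine kinase inhibitor entries beside it give a plain 2-week limit with no condition.

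Item 3.2.8, on major surgery, handles the same two ideas differently. It bars anyone operated on no more than 2 "weeks prior to starting study drug or who have not recovered from side effects of such therapy".

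The population is pretreated: "Patients must have received at least one prior line of therapy for their advanced lung cancer" (Section 3.1.3), with no upper limit on the number of lines. At registration, "A member of the study team will confirm eligibility criteria and complete the protocol-specific eligibility checklist" (Section 4.1), and "The QACT Registrar will (a) validate eligibility, (b) register the participant on the study" (Section 4.2). On the first dosing day, "The patient should continue to meet all eligibility criteria on C1D1, as they did during the screening period" (Section 5.1.1).

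**The concern.** A clause beginning with *if* and describing recovery belongs to a permission. Here it hangs on an exclusion, which turns its effect round: recovery becomes the reason for barring a patient, and lack of recovery takes the patient outside the rule. The entry also says nothing about someone whose last chemotherapy was more than 2 weeks ago and whose toxicity persists.

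The rule applies to every candidate whose earlier treatment included chemotherapy or an antibody. At stake is whether patients start AUY922 with unresolved toxicity from earlier treatment. Safety and tolerability are a secondary objective, and Section 13.5 puts all patients in the safety analyses.

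**Working it through.** No figure in the plan depends on this wording, so the check is mainly a reading of the criteria.

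**Step 1. What each reading excludes.** Classify patients by time since chemotherapy or antibody and by whether toxicity has resolved to grade 1 or lower.

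| Patient type | As written | Recovery waives washout (*unless* for *if*) | Both washout and recovery required |
|---|---|---|---|
| Within 2 weeks, resolved | excluded | not excluded | excluded |
| Within 2 weeks, unresolved | **not excluded** | excluded | excluded |
| Beyond 2 weeks, resolved | not excluded | not excluded | not excluded |
| Beyond 2 weeks, unresolved | **not excluded** | not excluded | excluded |

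The two corrections that a reader might make agree on the second and third rows and differ on the first and fourth.

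**Step 2. Which meaning is likely.** Requiring both fits the prohibiting lead-in, the unconditional 2-week limits next to it, and the form of 3.2.8. A waiver needs *if* to be replaced by *unless* and goes against the lead-in. So both-required is the likely intent, though the text does not state it.

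**Step 3. Whether another rule closes the gap.**
- Section 3.1.7 limits listed laboratory values, 3.1.10 deals with the eyes, 3.2.6 with diarrhea only, and 3.2.8 with recovery from surgery only.
- ECOG status of 2 or better (3.1.6) bounds fatigue loosely. Item 3.2.12, on uncontrolled intercurrent illness, may catch serious cases by judgment but sets no grade.
- Section 5.1.1 only re-applies the same criteria on day 1.
- Section 5.1.2 covers later doses, starts at grade 3, and accepts a return to baseline, which a carried-in toxicity already meets.
- Table 5 maintains the dose for grade 1 or 2 events in its residual category of other adverse events.

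What is left is unresolved toxicity of grade 2 or higher outside these areas. Neuropathy, mucositis and rash are examples. A patient with persistent grade 2 neuropathy from chemotherapy is eligible as written and ineligible under the likely intent.

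**Step 4. What a corrected rule must not contradict.** Section 3.1.7 allows AST and ALT up to 5.0 x "Upper Limit of Normal (ULN) if liver metastases are present", while Table 5 calls ALT above 3.0 and up to 5.0 x ULN grade 2. A bare grade 1 requirement would therefore conflict with 3.1.7. Section 3.1.10 likewise lets the principal investigator admit some patients with significant ocular abnormalities. Exempting all laboratory values would go too far: sodium, phosphorus, alkaline phosphatase and coagulation are measured (Table 6 and its notes) but have no limit in 3.1.7. The exception should apply parameter by parameter.

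**Step 5. Effect on the design.** Section 13.2 uses 10 + 19 = 29 patients, continues with at least 1 success in the first 10, and calls the result positive with at least 4 in 29. The probability of a positive result at true rate p is

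Σ (x = 1 to 10) C(10, x) pˣ (1 − p)¹⁰⁻ˣ × P[Bin(19, p) ≥ max(0, 4 − x)].

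At p = 0.05 this is 0.0468 (stated 0.047). At p = 0.20 it is 0.8011, so the type II error is 1 − 0.8011 = 0.1989 (stated 0.199). Both reproduce, and neither involves the eligibility wording.

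**The case against.** The strongest reply is that nobody would follow the literal text. A clinician would take the entry to mean that 2 weeks is long enough provided toxicity has settled, which is the both-required reading. Three clinics take part, with central registration and validation against a checklist, so one working rule may already be in use. The toxicities left after the other criteria are limited. The radiation, EGFR inhibitor and small-molecule entries carry no recovery clause either, so the protocol evidently tolerates some carried-in toxicity.

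Much of this stands. It limits the practical effect and is why the number affected is probably small. It does not make the text right. The checklist is not in the documents, so it cannot be relied on to cure the rule. For the neighbouring therapies the protocol sets no recovery standard; for chemotherapy and antibodies it names one, grade 1 or lower, and then words it so that it does not operate.

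A reader might infer more from the table in the working: that half of candidates are classified ambiguously, or that unrecovered patients have been enrolled. The documents support neither. The rows are logical types, not proportions, and nothing shows how sites applied the rule.

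A reader might also see a firm safety gap in 3.2.11, where history *and* presence of arrhythmia could be read as requiring both. That is probably loose drafting for two excluded categories. The other-heart-disease item, the long-QT and QTcF items and the QT-drug item in the same list, with 3.2.12, narrow what remains.

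**Conclusion.** The concern holds as a drafting error in an operative eligibility criterion, and it should be corrected. As written, the chemotherapy and antibody entry of 3.2.1 does not exclude a patient treated within 2 weeks whose toxicity is unresolved, and sets no recovery requirement for patients treated earlier. No other criterion or dosing rule fully replaces it.

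That both washout and recovery were intended is an inference from the lead-in, the adjacent entries and 3.2.8; the sponsor has to confirm it. The documents give no count of affected patients. Sample size, decision rule and error rates are untouched. The wording of 3.2.11 is a minor, separate point.

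**What to change.** Reword the entry in the form that 3.2.8 already uses, for example:

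> *Cytotoxic chemotherapy or a monoclonal antibody within 2 weeks, or toxicities from such therapy that have not resolved to ≤ grade 1 before study treatment starts (except where 3.1.7 or 3.1.10 sets a specific limit for that parameter).*

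This excludes the three patient types in the last column of the table. Item 3.2.6 remains the stricter rule for diarrhea. The sponsor should confirm that recovery does not waive the washout; if a waiver was meant, *unless* should replace *if*. The eligibility checklist should then be matched to the protocol text.

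Separately, in the arrhythmia entry of 3.2.11, replace *and* with *or* between history and presence. Keep atrial fibrillation and flutter in the entry, so that the exclusion is not loosened.

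The cost is one reworded entry, one changed word, one sponsor confirmation and a checklist comparison. A few patients with a rare mutation may become ineligible. No recalculation is needed.

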3.2.3 No prior treatment with any HSP90 or HDAC inhibitor compound is allowed

3.2.4 Participants with known and untreated brain metastases are excluded. Note: Patients without known prior CNS metastases and without clinical signs and symptoms of CNS involvement are not required to have an MRI of the brain prior to enrollment. **Patients with treated brain metastases**

**that are asymptomatic and clinically stable for two weeks will be eligible for protocol participation.**

- 3.2.5 History of allergic reactions attributed to compounds of similar chemical or biologic composition to AUY922
- 3.2.6 Unresolved diarrhea  $\geq$  CTCAE version 4, grade 1.
- 3.2.7 Pregnant or lactating women
- 3.2.8 Participants who have undergone any major surgery  $\leq$  2 weeks prior to starting study drug or who have not recovered from side effects of such therapy
- 3.2.9 Participants with known disorders due to a deficiency in bilirubin glucuronidation (e.g. Gilbert's syndrome).
- 3.2.10 Participants requiring the use of therapeutic doses of warfarin (Coumadin).
- 3.2.11 Participants with any of the following cardiac conditions:
  - History of long QT syndrome.
  - QTcF  $\geq$  450 ms during screening ECG.
  - History of clinically manifest ischemic heart disease including myocardial infarction, stable or unstable angina pectoris, coronary arteriography or cardiac stress testing/imaging with findings consistent with infarction or clinically significant coronary occlusion  $\leq$  6 months prior to study start.
  - History of heart failure or left ventricular (LV) dysfunction (LVEF  $\leq$  45%) by MUGA or ECHO.
  - Clinically significant ECG abnormalities including one or more of the following: left bundle branch block (LBBB), right bundle branch block (RBBB) with left anterior hemiblock (LAHB). ST segment elevations or depressions  $>$  1mm, or 2nd (Mobitz II) or 3rd degree AV block.
  - History and presence of atrial fibrillation, atrial flutter or ventricular arrhythmias including ventricular tachycardia or Torsades de Pointes.
  - Other clinically significant heart disease (e.g. congestive heart failure, uncontrolled hypertension, history of labile hypertension, or history of poor compliance with an hypertensive regimen).
  - Clinically significant resting bradycardia (<50 beats per minute).
  - Patients who are currently receiving treatment with any medication which has a relative risk or prolonging the QTc interval or inducing Torsades de Pointes (as listed in protocol section 5.4) and cannot be switched or discontinued to an alternative drug prior to commencing AUY922 dosing.
  - Patients who are on a cardiac pacemaker.

- 3.2.12 Uncontrolled intercurrent illness including, but not limited to ongoing or active infection, symptomatic congestive heart failure, unstable angina pectoris, cardiac arrhythmia, or psychiatric illness/social situations that would limit compliance with study requirements.
- 3.2.13 Concurrent malignancies or invasive cancers diagnosed within the past 3 years, except for adequately treated basal cell cancer of the skin or in situ cancer of the cervix.
- 3.2.14 Patients known to be HIV positive, because of the potential for pharmacokinetic interactions with AUY922 and increased risk of life-threatening infections. HIV testing is not required in the absence of clinical signs and symptoms suggesting HIV infection.

### **3.3 Inclusion of Women, Minorities and Other Underrepresented Populations**

Lung cancer affects men and women, and people of all race and socioeconomic class. We do not expect the inclusion and exclusion criteria to negatively affect enrollment of underrepresented populations.

## **4. REGISTRATION PROCEDURES**

### **4.1 General Guidelines for DF/HCC and DF/PCC Institutions**

Institutions will register eligible participants with the DF/HCC Quality Assurance Office for Clinical Trials (QACT) central registration system. Registration must occur prior to the initiation of therapy. Any participant not registered to the protocol before treatment begins will be considered ineligible and registration will be denied.

A member of the study team will confirm eligibility criteria and complete the protocol-specific eligibility checklist.

Following registration, participants may begin protocol treatment. Issues that would cause treatment delays should be discussed with the Principal Investigator. If a participant does not receive protocol therapy following registration, the participant's protocol status must be changed. Notify the QACT Registrar of participant status changes as soon as possible.

### **4.2 Registration Process for DF/HCC and DF/PCC Institutions**

The QACT registration staff is accessible on Monday through Friday, from 8:00 AM to 5:00 PM Eastern Standard Time. In emergency situations when a participant must begin treatment during off-hours or holidays, call the QACT registration line at [REDACTED] and follow the instructions for registering participants after hours.

The registration procedures are as follows:

1. Obtain written informed consent from the participant prior to the performance of any study related procedures or assessments.
2. Complete the protocol-specific eligibility checklist using the eligibility assessment documented in the participant's medical/research record. **To be eligible for registration to the study, the participant must meet each inclusion and exclusion criteria listed on the eligibility checklist.**

**Reminder:** Confirm eligibility for ancillary studies at the same time as eligibility for the treatment study. Registration to both treatment and ancillary studies will not be completed if eligibility requirements are not met for all studies.

3. Fax the eligibility checklist(s) and all pages of the consent form(s) to the QACT at [REDACTED]

**Exception:** DF/PCC Affiliate sites must fax the entire signed consent form including HIPAA Privacy Authorization and the eligibility checklist to the Network Affiliate Office. The Network Affiliate Office will register the participant with the QACT.

4. The QACT Registrar will (a) validate eligibility, (b) register the participant on the study, and (c) randomize the participant when applicable.
5. The QACT Registrar will send an email confirmation of the registration and/or randomization to the person initiating the registration immediately following the registration and/or randomization.

#### 4.3 General Guidelines for Other Participating Institutions

N/A

#### 4.4 Registration Process for Other Participating Institutions

N/A

### 5. TREATMENT PLAN

Treatment will be administered on an outpatient basis. Expected toxicities and potential risks as well as dose modifications for AUY922 are described in Section 6 (Expected Toxicities and Dosing Delays/Dose Modification). No investigational or commercial agents or therapies other than those described below may be administered with the intent to treat the participant's malignancy.

This is a single-arm, open-label, phase II trial of AUY922. All patients will receive the same dose and schedule of study medication, which is:

